In the event that any patient permanently discontinues the study treatment, regardless of reason, reasonable efforts should be made to have the patient return for an early termination visit and have the End of Treatment evaluations completed as described in [Section 8](#). All patients completing/discontinuing study treatment at any time point will be followed in the Long-term follow-up period until they reach 2 years from Day 1.

The date any patient discontinued the study treatment and the specific reason for discontinuation will be recorded in the eCRF.

Table 6-3 Criteria for interruption and re-initiation of ruxolitinib treatment for adverse events suspected to be drug-related

Dose modifications for ruxolitinib for adverse events suspected to be drug-related	
Worst toxicity	
Investigations (Hematologic)	
Neutropenia (ANC)	
Grade 1 (ANC < LLN - 1500/mm3)	Recommendation: Maintain dose level
Grade 2 (ANC < 1500 - 1000/mm3)	Recommendation: Maintain dose level
Grade 3 (ANC < 1000 - 750/mm3)	Recommendation: Maintain dose level
Grade 3 (ANC < 750 - 500/mm3)	Mandatory: Reduce 1 dose level (see Table 6-4), monitor ANC daily until resolved to ≤ Grade 2, then resume initial dose level
Grade 4 (ANC < 500/mm3)	Mandatory: Hold dose, monitor ANC daily until resolved to ≤ Grade 3, then resume at reduced 1 dose level (Table 6-4). If resolves to ≤ Grade 2, can resume initial dose level. If not resolved in ≤14 days the patient must be discontinued.
Febrile neutropenia (ANC < 750/mm3, fever ≥ 38.5°C)	Mandatory: Hold dose until resolved, then restart at reduced 1 dose level
Thrombocytopenia	
Grade 1 (PLT < LLN-75,000/mm3)	Recommendation: Maintain dose level
Grade 2 (PLT < 75,000 - 50,000/mm3)	Recommendation: Maintain dose level
Grade 3 (PLT < 50,000 - 25,000/mm3)	Recommendation: Maintain dose level
Grade 4 (PLT < 25,000 - 20,000/mm3)	Recommendation: Maintain dose level
Grade 4 (PLT < 20,000 - 15,000/mm3)	Mandatory: Reduce 1 dose level until resolved to ≥20,000/mm3 If resolved in ≤ 7 days, then resume initial dose level If resolved in > 7 days, then maintain at reduced 1 dose level

Dose modifications for ruxolitinib for adverse events suspected to be drug-related	
Worst toxicity	
Grade 4 (PLT < 15,000/mm ³)	Mandatory: Hold dose until resolved to $\geq 20,000/\text{mm}^3$, then resume at reduced 1 dose level. If resolves to \leq Grade 3, can resume initial dose level. If not resolved in ≤ 14 days the patient must be discontinued.
Investigations (Renal)	
Serum creatinine	

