4. As applicable, Pregnancy Outcomes Reporting Consent for female subjects

Females of child bearing potential should be informed that taking the study medication may involve unknown risks to the fetus if pregnancy were to occur during the study and agree that in order to participate in the study they must adhere to the contraception requirement for the duration of the study. If there is any question that the patient will not reliably comply, they should not be entered in the study.

As per [Section 4.6](#), during a public health emergency as declared by local or regional authorities i.e. pandemic, epidemic or natural disaster, that may challenge the ability to obtain a standard written informed consent due to limits that prevent an on-site visit, Investigator may conduct the informed consent discussion remotely (e.g. telephone, videoconference) if allowable by a local health authority.

Guidance issued by local regulatory bodies on this aspect prevail and must be implemented and appropriately documented (e.g. the presence of an impartial witness, sign/dating separate ICFs by the patients and person obtaining informed consent, etc.).

8 Visit schedule and assessments

The assessment schedule ([Table 8-1](#)) lists all of the assessments and indicates with an “X”, the visits when they are performed. All data obtained from these assessments must be supported in the subject’s source documentation.

Patients should be seen for all visits/assessments as outlined in the assessment schedule ([Table 8-1](#)) or as close to the designated day/time as possible. (Refer to [Section 8.3](#).) Missed or rescheduled visits should not lead to automatic discontinuation. Patients who discontinue from study treatment are to return for the end of treatment visit as soon as possible, and attend the follow-up visits as indicated in the Assessment Schedule.

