Patients who discontinue from study or withdraw their consent/oppose the use of their data/biological samples should be scheduled for a final evaluation visit if they agree, as soon as possible, at which time all of the assessments listed for the final visit will be performed. At this final visit, all dispensed investigational product should be reconciled, and the adverse event and concomitant medications not previously reported must be recorded on the CRF. As per [Section 4.6](#), during a Public Health emergency as declared by Local or Regional authorities i.e. pandemic, epidemic or natural disaster that limits or prevents on-site study visits, alternative methods of providing continuing care may be implemented by the investigator as the situation dictates.

Table 8-1 Assessment Schedule

Period	Screening	Treatment ¹					Safety Follow-up	Long Term Follow-up ²		
Visit Name	Screening	Day 1	Week 1-Week 8 (Weekly)	Week 12-Week 24 (Monthly)	Week 28-Week 48 (only in the case of taper or aGvHD flare, monthly)	EOT (Week 24/Week 48) ³	Safety Follow-up visit	Month 12	Month 18	Month 24
Weeks	-4	1	1 to 8	12 to 24	28 to 48	48	0	53	78	105
Days	-28 to -1	1	7 to 56	84 to 168	196 to 336	-	Last dose [contact]
Study Informed Consent/Assent	X									
Inclusion / Exclusion criteria	X									
Disease history (alloSCT and aGvHD history, CIBMTR risk assessment)	X									
HCT-Specific Co-Morbidity Index Score	X									
Demography	X									
Other relevant Medical History	X									
Prior/Concomitant Medications	X (From screening until safety follow up)									
IWRS/IRT (Registration, EOT)	X	X	X (Monthly)	X	X	X				
Physical Examination	S	S	S	S	S	S				
Body Height	X	X		X (Week 24)		X		X	X	X
Body Weight	X	X	X	X	X	X		X	X	X
Vital Signs	X	X	X	X	X	X				
Hematology	X	X	X	X	X	X				
Chemistry	X	X	X	X	X	X				

Period	Screening	Treatment ¹					Safety Follow-up	Long Term Follow-up ²		
Visit Name	Screening	Day 1	Week 1- Week 8 (Weekly)	Week 12- Week 24 (Monthly)	Week 28- Week 48 (only in the case of taper or aGvHD flare, monthly)	EOT (Week 24/Week 48) ³	Safety Follow-up visit	Month 12	Month 18	Month 24
Weeks	-4	1	1 to 8	12 to 24	28 to 48	48	0	53	78	105
Days	-28 to -1	1	7 to 56	84 to 168	196 to 336	-	Last dose [contact]
Coagulation	X	X	X	X	X	X				
Hepatitis viral serology testing (HBV, HCV)	X									
Hepatitis viral load (HBV, HCV)	X	X (Every 6 months while on ruxolitinib treatment)								
Urinalysis	X	X	X	X	X	X				
Pregnancy test (serum)	S ⁵					S ⁵	S ⁵			

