Pregnancy Test (urine)		S ⁵	S (monthly) ⁵							
acute GvHD staging	X	X								
aGvHD Response assessment			X	X	X	X				
Chronic GvHD assessment			X (Monthly)			X		X	X	X
Hematologic disease relapse/progression assessment		X	X	X	X	X		X	X	X
Second primary malignancy assessment		X	X	X	X	X		X	X	X
Graft Failure Assessment	X		X (Monthly)			X		X	X	X
Adverse Events		X (From screening until safety follow up)								
Treatment Acceptability and Palatability questionnaire ⁶		X (post dose)	X (Only week 4)	X (Only week 24)						
Study Treatment administration		X	X	X	X					

Period	Screening	Treatment ¹					Safety Follow-up	Long Term Follow-up ²		
Visit Name	Screening	Day 1	Week 1- Week 8 (Weekly)	Week 12- Week 24 (Monthly)	Week 28- Week 48 (only in the case of taper or aGvHD flare, monthly)	EOT (Week 24/Week 48) ³	Safety Follow-up visit	Month 12	Month 18	Month 24
Weeks	-4	1	1 to 8	12 to 24	28 to 48	48	0	53	78	105
Days	-28 to -1	1	7 to 56	84 to 168	196 to 336	-	Last dose [contact]
PK blood sampling		X (see Section 8.6.1.1)	X (See Section 8.6.1.1)	X (See Section 8.6.1.1)						
Survival Follow-up								X	X	X
Disposition						X				

^X Assessment to be recorded in the clinical database or received electronically from a vendor

^S Assessment to be recorded in the source documentation only

¹ From Day 1 to Week 24/End of Study Treatment (EOT) Weekly visits from Week 1 to Week 8 (Day 56) Monthly visit (every 28 days) after Day 56 until Week 24 or EOT, whichever occurs later

² (See [Section 9.1.5](#) for details)

³ EOT visit occurs when the patient discontinues study treatment. If EOT occurs before Week 24 the patient will still follow the visit schedule as planned and then continue to the follow up phase.

⁵ For applicable female patients only ([Section 8.5.5](#)). Per Investigator discretion, a serum pregnancy test can be performed in lieu of a urine pregnancy test.

⁶ Only for patients administered with oral pediatric formulation starting treatment Day 1 ([Section 8.6.3.1](#))

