9.1 Discontinuation from study treatment and from study

9.1.1 Discontinuation of study treatment

Patients may voluntarily discontinue from the study treatment for any reason at any time. If a patient decides to discontinue from the study treatment the investigator should make a reasonable effort (e.g. telephone, e-mail, letter) to understand the primary reason for this decision and record this information in the patient's chart and on the appropriate CRF pages. They may be considered withdrawn if they state an intention to withdraw, fail to return for visits, or become lost to follow-up for any other reason.

The investigator may discontinue study treatment for a given patient if, he/she believes that continuation would be detrimental to the patient's well-being.

In addition to mandatory discontinuation from study treatment listed in [Table 6-3](#), discontinuation from study treatment is required under any of the following circumstances:

1. Lack of response of aGvHD treatment at Day 28 ([Section 6.1.5](#)) ([Section 12.4.1](#))
2. Patients requiring new systemic therapy for aGvHD at any time ([Section 6.1.5.1.1](#))
3. aGvHD flare occurring during ruxolitinib taper after Week 24 ([Section 6.1.5.1.1](#))
4. Development of signs or symptoms of cGvHD including *de novo*, overlap, or progressive onset ([Section 8.4.1.3](#))
5. Underlying hematological disease progression or relapse ([Section 8.4.1.5](#))
6. Evidence of graft failure necessitating rapid taper of immunosuppression, administration of non-scheduled DLI, stem cell boost, chemotherapy, or other treatment that would expectedly affect aGvHD,
7. Adverse events leading to discontinuation from study treatment ([Section 6.5.2](#))
8. Pregnancy ([Section 8.5.5](#))
9. Protocol deviation that results in a significant risk to the patient's safety including use of prohibited treatment ([Section 6.2.2](#))
10. Patient has not weaned off corticosteroids, CNIs and ruxolitinib by Week 48 ([Section 6.1.5.1](#).)

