Patients who discontinue ruxolitinib study treatment for reasons other than achieving a CR or PR should NOT be considered withdrawn from the study and will enter the Long Term Follow-Up after completion of the Safety Follow Up visit [Section 9.1.5](#) and assessments at the end of Week 24. All other patients (including patients that discontinue ruxolitinib prior to Week 24 for achieving a CR or PR) will enter Long-term follow-up and continue to follow the Visit Evaluation Schedule as outlined in the [Table 8-1](#). Patients who develop cGvHD must discontinue from the study, and may utilize a ruxolitinib tapering strategy per [Section 6.1.5.1](#). Patients with hematologic disease progression, graft failure, AE, patient safety, or pregnancy may require abrupt cessation of ruxolitinib study treatment per Investigator discretion. Patients should return for assessments as specified at the EOT visit in [Table 8-1](#). The investigator must also contact the IRT to register the patient's discontinuation from study treatment.

If they fail to return for these assessments for unknown reasons, every effort (e.g. telephone, email, letter) should be made to contact them as specified in [Section 9.1.5](#).

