9.1.5 Follow up for safety evaluations

1. Safety Follow-up Visit

All patients must have a follow-up visit for safety evaluations 30 days (+ 3 day visit window) following the last dose of study treatment based on discontinuation from Treatment Period.

At the Safety Follow-Up visit, adverse events and therapies after treatment discontinuation will be reviewed. In addition, serum pregnancy will be collected for female patients of child-bearing potential. Refer to [Table 8-1](#). Patients who remain on ruxolitinib at Week 48 and obtain access to ruxolitinib outside of the study will not complete the safety follow-up visit since study treatment will continue.

1. Long-term safety Follow-up

All patients who discontinue study treatment (responders, non-responders, completing or prematurely discontinued from treatment period for any reasons as outlined above) will enter in the Long Term Follow-Up period, which lasts up to 24 months from start of study treatment (Day 1). Patients who prematurely discontinue ruxolitinib prior to Week 24 (without achieving CR or PR), must have assessments performed at the end of Week 24 ([Table 8-1](#)) and subsequently enter the Long Term follow-up period.

Visits are scheduled every six months (+/- 1 month from scheduled visit) starting Month 12 followed by subsequent visits at Month 18 and Month 24. Patients who may have an End of Treatment at Week 48 due to extended taper or aGvHD flare, will have the long-term follow up at Month 18 and 24 only.

Information to be collected during Long-Term follow-up is detailed in [Table 8-1](#). Data collected should be entered in the appropriate eCRF. Unscheduled visits may be performed as necessary. Additional assessments may be done as per institutional guidelines at investigator's discretion at any time during the trial.

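### Protocol Section 9.1.1 tells sites that patients with chronic GvHD leave the study, where the rest of the protocol has them leave study treatment and stay in follow-up

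*Protocol*

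**What the plan says.** Protocol Section 9.1.1 is headed as discontinuation of study treatment. Its list is introduced by "discontinuation from study treatment is required under any of the following circumstances", and item 4 is the development of cGvHD. The paragraph after the list begins with patients who stop ruxolitinib for reasons other than achieving CR or PR. They "should NOT be considered withdrawn from the study and will enter the Long Term Follow-Up". A few lines later the same paragraph says: "Patients who develop cGvHD must discontinue from the study, and may utilize a ruxolitinib tapering strategy".

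Protocol Section 8 gives the two kinds of exit different consequences. After stopping ruxolitinib, a patient must "return for the end of treatment visit as soon as possible, and attend the follow-up visits as indicated in the Assessment Schedule". The next paragraph has a different rule: "Patients who discontinue from study or withdraw their consent/oppose the use of their data/biological samples should be scheduled for a final evaluation visit".

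Other places deal with follow-up after treatment stops:
- Section 6.5.2.1.2: patients who complete or stop treatment at any time "will be followed in the Long-term follow-up period until they reach 2 years from Day 1".
- Table 8-1, footnote 3: if treatment ends before Week 24, "the patient will still follow the visit schedule as planned and then continue to the follow up phase".
- Section 9.1.5: all who stop treatment, for whatever reason, "will enter in the Long Term Follow-Up period, which lasts up to 24 months from start of study treatment".
- Section 3.3: all patients are followed for survival, relapse, graft failure, cGvHD and second malignancy, whenever treatment stopped.

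**The concern.** The sentence is a mandatory instruction to sites, and it names the wrong kind of exit. Read alone, it ends participation because of a disease event that occurs after baseline and that the protocol expects to be common.

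The endpoints at stake are those that need observation after cGvHD. Protocol Section 12.5.1 and SAP Section 3.7.1 censor OS, EFS, NRM and malignancy relapse at the last date the patient was known to be alive. None of the four treats cGvHD as an event or a competing risk. A patient closed out after cGvHD would therefore be censored early, and the 12-, 18- and 24-month estimates would lose that patient. Later graft-failure and second-malignancy data would go too, although Section 12.5.2 summarizes second malignancies over the whole study period.

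**Working it through.** **Step 1. Is the sentence wrong as written?**

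| Place in protocol | What happens to a patient who stops ruxolitinib |
|---|---|
| 9.1.1, item 4 | cGvHD: stop study treatment |
| 9.1.1, opening of the following paragraph | Stopped for a reason other than CR/PR: not withdrawn, enters long-term follow-up |
| 3.3, 6.5.2.1.2, Table 8-1 footnote 3, 9.1.5 | Followed to Month 24 |
| 9.1.1, cGvHD sentence | Leaves the study |

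The last row conflicts with every other row. The two terms are not interchangeable. The glossary says that a patient who discontinues study treatment still agrees to follow-up, and that after premature withdrawal no further assessments are planned. Section 8 prescribes different visits for each. The cGvHD sentence also allows a ruxolitinib taper, which makes sense only for a patient still under study care. So study treatment is meant.

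**Step 2. Which endpoints depend on it?** Day 28 ORR is settled early, and Section 8.4.1.2 places cGvHD after Day 56. Duration of response and FFS already treat cGvHD onset as a competing risk, so they need no later data. Cumulative incidence of cGvHD is reached at onset. That leaves OS, EFS, NRM and malignancy relapse, together with graft failure and second malignancies.

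**Step 3. How large could the loss of precision be for Month 24 OS?** The plan gives no figure to reproduce.

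Inputs from the documents:
- n = 45 (Section 12.8.1).
- cGvHD in up to 50% of patients, with no time horizon (Section 8.4.1.2).
- Planned treatment of 24 weeks, with a maximum of 48 weeks (Section 6.1.5.1).

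Assumptions not in the documents:
- Constant hazards, with the same death hazard before and after cGvHD.
- 24-month OS S0 = 0.65.
- 24-month cGvHD incidence p of 20% or 50%.
- Every patient on drug up to time T, and every patient with onset before T leaves at onset.

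Formulas:
- Death hazard: λ = −ln(0.65)/24 = 0.01795 per month.
- cGvHD hazard: μ solves μ/(μ+λ) × (1 − exp(−24(μ+λ))) = p. This gives μ = 0.01164 for 20% and 0.03778 for 50%.
- T = 24 weeks = 5.52 months, or 48 weeks = 11.04 months.
- Onsets before T = 45 × μ/(μ+λ) × (1 − exp(−T(μ+λ))).
- At risk at Month 24 = 45 × 0.65 × exp(−μT).
- 95% half-width = 1.96 × 0.65 × √(∫₀²⁴ λ/(45π(t)) dt), with π(t) = exp(−λt − μ·min(t,T)).

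Check with full follow-up: 45 × 0.65 = 29.25 at risk, and 1.96 × √(0.65 × 0.35/45) = 13.9 points.

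| Exits covered | cGvHD by Month 24 | Onsets before T | At risk at Month 24 | 95% half-width (points) |
|---|---|---|---|---|
| None | – | – | 29.25 | 13.9 |
| On drug, before Week 24 | 20% | 2.7 | 27.4 | 14.3 |
| On drug, before Week 24 | 50% | 8.1 | 23.7 | 15.3 |
| On drug, before Week 48 | 20% | 4.9 | 25.7 | 14.7 |
| On drug, before Week 48 | 50% | 14.0 | 19.3 | 16.5 |

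Varying S0 from 0.50 to 0.80 moves the onsets before Week 24 to 2.5-2.9 (20%) or 7.4-9.0 (50%). Onsets before Week 48 become 4.7-5.3 or 13.2-15.1.

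These are upper figures. Many patients will be off drug before T, and exit would fall after onset. Starting the cGvHD hazard at Day 56, in line with Section 8.4.1.2, cuts the onsets before Week 24 at S0 = 0.65 from 2.7-8.1 to about 2.0-6.1.

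**The case against.** The best reply is that the protocol resolves the matter itself. The section heading, item 4, the opening of the paragraph, the taper in the same sentence and four separate follow-up rules all point one way. The same paragraph goes on to send patients to the end-of-treatment visit and has the site register discontinuation from study treatment. A site would have to overlook all of that. This stands as an argument about likelihood and severity. It does not make the sentence right, and recoverable intent does not show how each site acted.

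Timing also limits the value of a text change. Enrolment was complete by 11 February 2021 (Amendment 3 rationale), and 48 weeks (336 days) later is 13 January 2022. Amendment 3 uses a template dated 14 January 2022. Essentially no patient could still be on study drug under the current wording. Whether the sentence stood in earlier versions cannot be seen. This stands, and it shifts the weight of the fix to the check on collected data.

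A reader might infer several stronger things that the documents do not support:
- **That follow-up was in fact cut short.** Nothing shows that any site did so.
- **That censoring falls at cGvHD onset.** SAP Section 3.1.1 uses the last contact date, drawn from many records. A taper, a final visit or the 30-day safety visit would place it later.
- **That every cGvHD onset to Month 24 is covered.** The sentence is about stopping and tapering drug, so the natural reading is patients on ruxolitinib.
- **That survival estimates are biased by some amount.** That depends on prognosis after cGvHD, which the documents do not give.

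**Conclusion.** The point holds as a minor internal inconsistency: one mandatory sentence is wrong as written and conflicts with its own section and with the follow-up rules elsewhere. If a site followed it literally for patients on drug, OS, EFS, NRM and malignancy relapse would be censored at last contact after cGvHD. Under the stated assumptions, the half-width for Month 24 OS would widen by at most about 0.4 to 2.6 points (14.3 − 13.9 to 16.5 − 13.9). These endpoints are descriptive, and Section 12.7 says that no efficacy hypothesis is tested. The primary endpoint, duration of response and FFS are essentially untouched. If sites kept following these patients, the effect is zero.

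**What to change.** In the cGvHD sentence of Section 9.1.1, have the patient discontinue from study treatment and enter Long-Term Follow-Up to Month 24. Keep the reference to Section 6.1.5.1, which is correct.

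Before database lock, list every patient whose study exit follows cGvHD onset. Where consent allows, obtain vital and relapse status to Month 24. This is the more useful half of the fix, because on-drug exposure under the current version is close to nil.

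The cost is one phrase and one listing. SAP Section 3.3.1 already tabulates study discontinuation with its reason, so the listing is a filter on data already held. The only real work is the status recovery, and that is needed only if the listing is not empty.

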9.1.1.1 Replacement policy

Patients who discontinue prematurely will not be replaced on this study.

9.1.2 Withdrawal of informed consent/ opposition to use data/biological samples

Patients may voluntarily withdraw consent to participate in the study for any reason at any time. Withdrawal of consent/ Opposition to use data/biological samples occurs only when a patient:

1. Explicitly requests to stop use of their biological samples and/or data (opposition to use patient's data and biological samples)

and

2. No longer wishes to receive study treatment

and

3. does not want to participate in the study any longer, and does not allow further collection of personal data.

This request should be in writing (depending on local regulations) and recorded in the source documentation.

Withdrawal of consent impacts ability to further contact the patient, collect follow up data (e.g. to respond to data queries) and potentially other country specific restrictions. It is therefore very important to ensure accurate recording of withdrawal vs. discontinuation based on the protocol definitions of these terms.

If a patient withdraws consent, the investigator should make a reasonable effort (e.g. telephone, e-mail, letter) to understand the primary reason for this decision to withdraw their consent/exercise data privacy rights and record this information. The investigator shall clearly document if the patient has withdrawn his/her consent for the use of data in addition to a study discontinuation.

Study treatment must be discontinued, and no further assessments conducted, and the data that would have been collected at subsequent visits will be considered missing.

Further attempts to contact the patient are not allowed unless safety findings require communication or follow up.

All efforts should be made to complete the assessments prior to study withdrawal. A final evaluation at the time of the patient's study withdrawal should be made as detailed in the assessment table.

For Japan: All biological samples not yet analyzed at the time of withdrawal may still be used for further testing/analysis in accordance with the terms of this protocol and of the informed consent form.

For EU and RoW: All biological samples not yet analyzed at the time of withdrawal will no longer be used, unless permitted by applicable law. They will be stored according to applicable legal requirements.

